Appendix C (The IRB-approved Protocol)

Figure 7. Summary of sample size

Sample size calculations for the overall difference between environmental exposures in green vs. comparison homes can be given as a simple test of two proportions and means; however a specific difficulty arises when trying to adjust for temporal and spatial correlations between measurements. A study that had enough measurements to assess spatial and temporal correlation was an integrated pest management (IPM) study conducted in New York City (Chew et al., 2006; Kass et al., 2009). We have used the design effect from this study to estimate the number of clusters (or buildings) needed to detect differences in cockroach allergen because IPM is also one of the main green characteristics in the Green Housing Study. Assumptions from the aforementioned study comparing IPM to non-IPM homes are listed below:

13 buildings

About half were treatment and the other half comparison

3 repeated measures at: baseline (before IPM), 3months later (post-IPM), and 6months later (post-IPM)

On average, 25 apartments within each building were measured

Appendix C (The IRB-approved Protocol)

For the comparison homes, the correlations between baseline and 3-month follow-up cockroach allergen measurements and 3-month and 6 months follow-up measurements were approximately equal to 0.5.

Design effect due to clustering = 3.62

Equation 1. Sample size for repeated measures – cockroach allergen.

$$m = D * [2(z_{\alpha} + z_{Q})^2 \{1 + (n - 1)\rho\}] / (n\Delta^2)$$

m = number in each group (e.g., intervention and non-intervention)

n = number of repeated measurements (equals 3 in this scenario)

z_{α} = Z score for alpha = 0.05

z_{Q} = Power, set at 0.80

ρ = correlation among repeated observations

$\Delta = d / \sigma$ where d is the smallest meaningful difference and σ is the standard deviation

D = Design effect due to clustering of apartments within buildings (This was not in the formula used by Diggle et al. (1994), but was added to adjust for clustering expected in our study.)

Note: we also assumed a design effect (e.g., increase (multiplicative) sample needed because of the effects of clustering) equal to 3.62. This is the ratio in clustering sampling variance divided by the simple random variance (of the same size) (i.e., the denominator without clustering taken into account).

When calculating the sample sizes, we used two standardized effect sizes based on the IPM study: 0.37 and 0.30. The effect size of 0.37 is based on the ability to detect a difference of 0.8148 ln units of the *Blattella germanica* cockroach allergen (i.e., Bla g 2) and a standard deviation of ~ 2.2. The effect size of 0.30 is based on the ability to detect a difference of 0.649 ln units of Bla g 2 and a standard deviation of 2.2. We also assumed an alpha of 0.05 and a power of 80%). The sample size based on changing the expected correlation between repeated measures would result is presented in Table 21.

Assuming a correlation of 0.5 we get the following:

With assumption 1, we would need 16 buildings (8 green and 8 comparison) with at least 25 apartments per building

With assumption 2, we would need 26 buildings (13 green and 13 comparison) with at least 25 apartments per building.

Appendix C (The IRB-approved Protocol)

Table 21. Sample size requirements for number of buildings.

Correlation between repeated measures	Sample size requirements (number of buildings)	
	Assuming Delta=0.377	Assuming Delta=0.30
0.2	6	9
0.3	7	11
0.4	8	12
0.5	8	13
0.6	9	15
0.7	10	16
0.8	11	17

*sample size is for each group (e.g., 8 buildings means 8 comparison and 8 green buildings)

We also estimated the sample size for detecting differences in pesticides and VOCs. To date, there is only one study of an intervention to decrease pesticide exposures that used objective measurements of pesticide levels in residential homes in a non-agricultural environment (Williams et al., 2006). This study was conducted in homes of Latina and African-American women living in low-income housing in New York. In the study, 25 homes underwent IPM as an intervention. The pesticide synergist, piperonyl butoxide, is unique to pyrethroid pesticides and this was an analyte that was measured in the study's air samples. We used their pre- and post piperonyl butoxide concentrations (pre = mean $1.66 \pm$ s.e. 0.71 ng/m^3 vs. post = mean $0.8 \pm$ s.e. 0.22 ng/m^3) for our calculations of sample size which are shown in Table 22.

To date, there is only one study comparing the VOC levels in newly-built green homes and conventionally-built homes; therefore, this was not a renovation like our proposed study. We calculated the sample size based on their measurements of formaldehyde in the two types of homes in their study. This study was conducted in Finland. In the study, 6 apartments in each type of building had air measurements for formaldehyde (green-built: mean = $13 \text{ } \mu\text{g/m}^3$, s.d. = 4 vs. conventionally-built: mean $23 \text{ } \mu\text{g/m}^3$, s.d. = 5). We calculated the sample size necessary to detect a decrease in 50%, 25%, and 15%, of the difference in formaldehyde levels observed in their two study groups (see Table 22).

Devos et al. (1990) have suggested that the minimum level of an indoor irritant be set with a safety factor of 40 (Devos, Patte et al., 1990). Given that the American Conference of Governmental Industrial Hygienists (ACGIH) threshold limit value is $368 \text{ } \mu\text{g/m}^3$, a minimum level of formaldehyde below which no irritant effects are expected is $9.8 \text{ } \mu\text{g/m}^3$ (which is the CDC/ATSDR Minimum Risk Level, <http://www.atsdr.cdc.gov/ToxProfiles/tp.asp?id=220&tid=39>).

Appendix C (The IRB-approved Protocol)

Table 22. Calculations of samples sizes for VOCs and pesticides

Analyte	Design Effect	Effect Size (Δ)	Required Sample size (in each group)
Formaldehyde			
- 15% : 1.5 $\mu\text{g}/\text{m}^3$	3.6	0.33	408
- 25% : 3.5 $\mu\text{g}/\text{m}^3$	3.6	0.77	75
- 50% : 5 $\mu\text{g}/\text{m}^3$	3.6	1.10	37
(based on Tuomainen et al., 2003)			
Piperonyl butoxide			
0.8 ng/m^3 decrease	3.6	0.33	418
(based on Williams et al., 2006)			

* $\alpha = 0.05$, $1-\beta = 0.80$

Summary of sample size for environmental exposures: Of the intervention studies relevant to green housing, the sample size calculations based upon the cockroach allergen intervention study provided the most information to inform our estimates of sample size required for the Green Housing Study. Because [name] was a co-author on the manuscript and had analyzed the cockroach allergen samples in her laboratory, she had access to the repeated measurements database and this helped to guide our design effect due to clustering of apartments within buildings. The other papers did not have repeated measurements (thus the variance estimates were rather wide) and they also had more restrictive groups (e.g., nonsmoking pregnant women, Finnish families living in newly-constructed apartments) than is planned in the Green Housing Study. Thus, we believe that our estimates are conservative.

Sample size for assessing asthma outcomes: The calculation for assessing differences in health markers were based upon a multi-site asthma intervention study (Morgan et al., 2004). In this study, 407 asthmatic children with the multi-factorial intervention (asthma trigger education, mattress covers, IPM, HEPA filter units) had fewer days (2.62 days \pm 0.12) than those (n=414) without the intervention (3.21 days \pm 0.13). Table 15 shows sample sizes with different assumptions of effect sizes using equation 2.

Equation 2. Sample size for asthma morbidity outcomes.

$$m = D * [2(z_{\alpha} + z_{\rho})^2 \{1 + (n - 1)\rho\}] / (n\Delta^2)$$

m = number in each group (e.g., intervention and non-intervention)

n = 1 (note: for differences of differences, we assumed a value of 1)

z_{α} = Z score for alpha = 0.05

z_{ρ} = Power, set at 0.80

ρ = correlation among repeated observations

Δ = d/σ where d is the smallest meaningful difference and σ is the standard deviation

D = Design effect due to clustering within 13 sites (This was not in the formula used by Diggle et al. (1994), but was added to adjust for clustering expected in our study.) Based upon the Kwon et al. (2003) paper that showed a design effect of 1.5 was helpful for designing cluster

Appendix C (The IRB-approved Protocol)

studies to assess asthma outcomes in national surveys (e.g., BRFSS and NHANES), we assumed a slightly smaller design effect equal 1.2 due to the expected low average number of children per cluster).

Table 23. Sample size requirements for number of children with asthma.

Effect size (i.e., delta)	Sample size requirements (number of asthmatic children)	
	in Green buildings	in Comparison buildings
0.20	274	274
0.232*	274	274
0.30	206	206
0.35	151	151
0.40	116	116

* Based on observed effect size from Morgan et al. (2004) study.

We used Equation 3 to calculate the sample size based on binary outcomes. The assumptions for the equation were based upon an intervention study in Seattle Public housing (Krieger et al., 2005). The Seattle researchers had n= 110 in a high-intensity intervention group and n = 104 in a low-intensity intervention group follow. They assessed the percentage of children in each group with urgent health service use in the past 2 months. Taking the difference between baseline and exit measurements of the two proportions for high-intensity (23.4% - 8.4% = 15% difference) and low-intensity (20.2% - 16.4% = 3.8% difference), we calculated n= 102 in each study group.

Equation 3. Sample size for binary asthma morbidity outcomes.

$$m = \left[\left[(z_{\alpha} \{ 2\bar{p}\bar{q} (1 + (n - 1)\rho) \})^2 + z_Q \{ (1 + (n - 1)\rho) (p_A q_A + p_B q_B) \}^2 \right]^{1/2} \right]^2 / nd^2$$

m = number in each group (e.g., intervention and non-intervention)

n = 1 (note: for differences of differences, we assumed a value of 1)

z_{α} = Z score for alpha = 0.05

z_Q = Power, set at 0.80

ρ = correlation among repeated observations

p_A = proportion of Group A

p_B = proportion of Group B

q_A = 1- proportion of Group A

q_B = 1- proportion of Group B

$$\bar{p} = \bar{p} = (p_A + p_B) / 2$$

$$\bar{q} = \bar{q} = 1 - \bar{p} = 1 - \bar{p}$$

d = is the smallest meaningful difference between proportions

D = Design effect due to clustering (This was not in the formula used by Diggle et al. (1994), but was added to adjust for clustering expected in our study.) Based upon the Kwon et al. paper (2003) that showed a design effect of 1.5 was helpful for designing cluster studies to assess asthma outcomes in national surveys (e.g., BRFSS and NHANES), we assumed a slightly smaller design effect equal 1.2 due to the expected low number of expected of average children per cluster).

Appendix C (The IRB-approved Protocol)

B.2. Procedures for the Collection of Information

The characteristics of study participants that will be included are: 1) Children age 7-12 years with asthma (note: The child must have been diagnosed with asthma by a physician and have had asthma-related symptoms (wheezing, slow play or night awakening) during the past 6 months), and 2) mothers/ primary caregivers of enrolled children. Also, the mother/ primary caregiver must speak English, Spanish, or Chinese to be included in the study and the enrolled participants must live in the home (from which environmental samples will be collected) on average 7 days per week.

Upon notification from HUD that a participating housing complex is about to begin rehabilitation, CDC will contact local academic institutions and departments of health in order to mobilize the Green Housing Study in that location. We envision that together with HUD and local academic investigators at the selected sites, CDC will convene town meetings at each participating complex to describe the study to residents, answer questions, and invite their participation. Depending upon the number of residents who initially volunteer at the town hall, we will convene additional town hall meetings to augment participation. Residents who express interest in the study can contact the site projector coordinator either at the town hall meetings or by telephone. Subsequently, the trained staff will schedule a home visit with the residents. For quality control purposes, teams of two trained staff will visit the home to collect questionnaire data via an in-person interview and perform environmental sampling. The environmental sampling technician will review the questionnaire information that the other technician obtained during the interview with the study participant. Also, the database entry screen will have validation checks (e.g., number of reported asthma symptoms cannot equal a negative number)

Statistical analysis: The main variable of interest is the type of home (green vs. comparison); however, there may be different permutations within green housing. For example, HUD has two levels of green which are based upon the acceptance of HUD-approved recommendations: Level 1) landlord agrees to implement at least 75% of the dollar amount of green repairs and improvements; and Level 2) landlord agrees to implement at least 50% of the dollar amount. While discretizing the green rehabilitation into Level 1 and Level 2 categories could simplify our analysis, we acknowledge that the two different levels do not necessarily capture green materials or practices that are potentially related to health. For example, a green home could have low VOC paint, or low VOC carpet, or replace the kitchen cabinets with low VOC materials, or have some combination of these activities.

Allergens in the homes: Variables related to indoor allergens in the homes may take the form of continuous measures of specific allergens or of indicator variables for the presence or absence of certain allergens or combinations of allergens. Allergen concentrations will be reported as μg of allergen per g of collected dust and μg of allergen per unit area vacuumed.

VOCs and pesticides in the homes: Variables related to VOCs (whether total or speciated) and pesticides (pyrethroids, propoxur, and piperonyl butoxide) in the homes may take the form of continuous measures or indicator variables for the presence or absence of certain chemicals or combinations of chemicals. Concentrations will be reported as ppm (and also $\mu\text{g}/\text{m}^3$) in the case of the VOCs and $\mu\text{g}/\text{g}$ in the case of the pesticides.

Appendix C (The IRB-approved Protocol)

Conditions of the home environments: Factors that may influence the presence and levels of allergens, VOCs, and pesticides include: the presence of carpets; pests; housing type and age, average winter temperature and relative humidity, air exchange rates.

Wheeze /asthma severity: This information may be used in the form of categorical and continuous variables (number of emergency room visits for asthma, use of asthma medications, lost school days). Nights awakened by asthma, and spirometry measurement such as FEV1 and FEF_{25-75%}).

Additional environmental and host factors for disposition to wheeze/asthma: Other risk factors for the main outcomes of interest include: environmental tobacco smoke; acute respiratory illnesses; gender; socioeconomic status of primary caregiver; degree of acculturation (operationalized); and deficiencies in access to and quality of health care. Many of these factors allow for a variety of formulations. Environmental tobacco smoke, for example, may be analyzed as an indicator variable for the presence or absence of smoking in the home, as count data for the number of smokers in the home, or as a continuous variable for the number of cigarettes smoked per day in the home. The choice of formulation of risk factors will be driven by the aim of clarifying the main relationships of interest, for example the role of allergens in the development of early allergic sensitization and asthmatic airways disorders.

Descriptive statistics: Study participants will be characterized with regard to demographic variables such as age, gender, and race; clinical variables such as symptom/medication use frequency, healthcare utilization, allergy sensitivity and pulmonary function, and environmental variables such as indoor allergens (cockroach, mouse, cat, and dust mite). Categorical variables will be summarized by frequencies, while continuous variables will be summarized by mean, standard deviation, median, and range. Levels of mold, indoor allergens, pesticides, and VOCs will be log-transformed to compute geometric means and geometric standard deviations. Where appropriate, other transformations or non-parametric analysis methods will be used.

Missing data: We anticipate the inevitable occurrence of missing data, including dropouts. First, if the missingness of the data is sufficiently small and the associations of interest are sufficiently large, the simple device of imputing upper and lower bound data, if possible, will suffice. That is, a small amount of missing data and a large effect size will allow a unique inference to stand no matter whether the missing data are imputed at their minimum or maximum possible values and used as such. This is consistent with the most conservative approaches adopted in clinical

Appendix C (The IRB-approved Protocol)

trials wherein subjects lost to follow-up are assumed to have died or to have otherwise suffered the worst possible endpoint. In general however, we must anticipate that we may be facing larger missingness and/or smaller effect sizes and/or impractical upper and lower bounds, such that primary inference changes between the extremes. In this case we will use the multiple imputation procedure of Rubin (Rubin, 1985) to address the problem. In this technique, a fair amount of effort is devoted to the construction of an imputation model or set of models to provide best estimates of missing endpoints. These best estimates may include the best case or worst case scenarios; the point is that they should most fairly represent data that are missing given the observable information at hand. The imputation models may need to assume data missing at random or they may need further specification to allow for non-ignorable missingness. Each analysis be developed using the best imputation model for missing data for that analysis, using available observed covariates and non-missing endpoints.

B.3. METHODS TO MAXIMIZE RESPONSE RATES AND DEAL WITH NONRESPONSE

Two large-scale housing intervention studies in low-income neighborhoods that had a 1-year follow-up have reported response rates of 92-93% (Morgan et al., 2004; Persky et al., 2009). We anticipate that once enrolled into the Green Housing study, participants will have at least an 80% response rate for completion of the 1-yr study.

We have two strategies to maximize response rates of the enrolled participants: 1) Study participants (mothers/ primary caregivers of children enrolled in study) will receive compensation for their participation as they complete the required study activities throughout the 1-year duration. (See section A.9 INCENTIVES FOR RESPONDENTS for details) and 2) We will also give study results to the participants. Other investigators have found that study participants often wish to know their results (Brody et al., 2007). By offering an in-person discussion of their results during their last home visit, we hope to maximize the chance for completion of their 1-yr follow-up. If we experience a loss-to-follow-up greater than 80%, our contingency plan is to meet with HUD partners to possibly add another study site.

We have the following instructions for trying to contact difficult-to-reach participants: 1) At least 10 attempts will be made and documented in an effort to reach the participant; 2) Calls and visits to the participants will be made at various times of days (mainly between 10am- 8pm) and on different days of the week at a time convenient to the study participant; 3) When leaving a message, the trained technician will leave his/her name, the name of his/her institution, the reason for the call (i.e., housing study, and the call-back number; and 4) The technician will try calling “alternate contacts” to reach the study participants.

B.4. TESTS OF PROCEDURES OR METHODS TO BE UNDERTAKEN

The Green Housing Study questionnaires were primarily based on questions from national health and housing surveys and different epidemiologic studies (e.g., The Inner-City Asthma Study, ICAS) that were conducted in different parts of the country among similar low-income, inner city children with asthma. The national surveys include the following:

The National Children’s Study (NCS)

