Appendix C (The IRB-approved Protocol)

Table 16. Questions of a possibly sensitive nature

Questions (possibly sensitive)	Specific uses of information
Which one or more of the following would you say is your race?	To adjust for race in statistical models.
What is the highest level of school that you have completed or the highest degree that you have received?	To adjust for socioeconomic status in statistical models.
Which category represents the total combined income of all members of this family during the past 12 months?	To adjust for socioeconomic status in statistical models.
Do you smoke cigarettes?	To adjust for smoking exposure in statistical models. Smoking could affect our environmental and clinical measurements.
During the past 6 months, how often have you seen cockroaches in your household?	To assess cockroach exposures pre- and post- interventions.
During the past 6 months, how often have you seen mice in your household?	To assess mouse exposures pre- and post-interventions.
During the past 6 months, how often have you seen rats in your household?	To assess rat exposures pre- and post-interventions.

Explanation given to respondents: These questions are needed for this study and some of them have been shown to be associated with environmental exposures and health outcomes, so we need to take them into account.

A.12 Estimates of Annualized Burden Hours and Costs

A. As discussed in the Background section of this ICR, we hypothesize that children ages 7-12 with asthma who live in green housing, will have improved health outcomes as compared to those who live in comparison housing. Consequently, the respondents that will complete the questionnaires are mothers/ primary caregivers of enrolled children with asthma (ages 7-12 years).

Approximately 1000 adults will complete the screening forms. Kass et al. (2009) obtained a screening percentage of 73% in their New York City Housing Authority intervention study. We estimate that after screening, 20% of households will not be eligible.

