Two large-scale housing intervention studies in low-income neighborhoods that had a 1-year follow-up have reported response rates of 92-93% (Morgan et al., 2004; Persky et al., 2009). With an anticipated loss to follow-up in our study of 20%, we will recruit 832 households with asthmatic children to end up with 650 enrolled children with asthma (ages 7-12 years) . All health and environmental exposure information about children will be provided by their mothers/ primary caregivers (i.e., no children will fill out questionnaires). For the purposes of assessing potential burden, we are using the maximum of 832 mothers/ primary caregivers

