Appendix C (The IRB-approved Protocol)

both the applicants of the HUD awards and the households themselves are self-selected. Specifically, the design does not allow generalizations based on city, type of locations (rural, suburban), climactic regions (e.g., desert, arctic), or ethnicities. Furthermore, this study will systematically exclude certain subsets of the population for logistical reasons. Specifically:

- i. Public housing is comprised mostly of 3 main ethnicities: white, African-American, and Latino (HUD, 2009).
- ii. Our main health endpoint, asthma, is highest among Latinos and African-Americans. While several childhood asthma studies have focused on some minority populations in the United States (African American and Latino), only recently have investigators focused studies of Asian populations. In the Boston Chinatown neighborhood, researchers found a higher prevalence of asthma for children born in the US as compared to those who were foreign-born in an Asian population, enriched with recent Chinese immigrants (Brugge et al., 2007). These results confirm findings in a similar Asian population from the same community (Greenfield et al., 2005).
- iii. We do not have the capacity to translate into all languages. However, we determined that it would be beneficial to include Spanish and Chinese translations for the reasons mentioned above. In meetings with stakeholders at our first potential study site, Boston, we found that they have a substantial Chinese population (along with Latino and African-American). The tenants' organization asked if we would recruit the Chinese residents too and if we could translate all of our materials into Chinese. We believe that the tenants' organization's request is reasonable. Furthermore, in other potential study site locations (e.g., Los Angeles, New York, San Francisco), Chinese language translation might also be relevant.

We assume an 80% participation rate for the eligible residents for the collection as a whole (as described in Part B, section 3).

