Appendix C (The IRB-approved Protocol)

measurements and health outcomes between the arms, we began by calculating sample sizes based on each of these measures.

Our sample calculations for environmental measurements (see Table 21) were based on cockroach allergen data in a repeated measures study of the effect of an integrated pest management (IPM) intervention, which indicate that 13 buildings would be necessary in each of the two arms of the study, assuming that 25 subjects could be recruited for each building, yielding 325 subjects/study arm to provide adequate statistical power for environmental measurements.

Our sample calculations for health outcomes (see Table 22) were based on asthma in children subjected to a multifactorial intervention (i.e., education, mattress covers, IPM, and HEPA filter units) in a repeated measures study. These data indicate that 274 subjects/study arm would be needed to provide adequate statistical power for asthma outcomes.

Therefore, since we desired sufficient power to detect meaningful differences in both 1) environmental measurements and 2) health outcomes, we selected the larger of the two estimates — 325 subjects/study arm — as the minimum sample size (see Figure 7). In addition, we augmented this number in order to account for an anticipated 20 percent loss to follow-up over a one-year period. After rounding up where necessary, this increased the sample size to 416 subjects/study arm, comprising 32 subjects (one subject per apartment) in each of 13 buildings in each study arm. The total sample size for the study across both study arms is 832 subjects. The details of our sample size calculations are listed below and the equations that were used were from a book on longitudinal data analysis by Diggle, Liang, and Zeger (1994).

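### The trigger for considering an extra study site is loss to follow-up above 80%, although the sample size is built on 20% loss and holds only up to 21.9%

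*Protocol*

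**What the plan says.** **Retention.** Appendix A, section B.3 expects that, once enrolled, "participants will have at least an 80% response rate for completion of the 1-yr study". It then gives the only numerical contingency for attrition: "If we experience a loss-to-follow-up greater than 80%, our contingency plan is to meet with HUD partners to possibly add another study site".

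**Sample size.** Section B.1 takes 325 per arm as the minimum and raises it to 416 per arm (32 in each of 13 buildings, 832 in total) to cover "an anticipated 20 percent loss to follow-up over a one-year period". Section A.12 repeats the planning figure: "With an anticipated loss to follow-up in our study of 20%, we will recruit 832 households", to finish with 650 children.

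**Screening.** Section A.12 also says "Approximately 1000 adults will complete the screening forms" and "We estimate that after screening, 20% of households will not be eligible". The burden table (Table 17) uses the same 1000 screened and 832 enrolled.

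**The concern.** Completion of 80% and loss of 80% are complements that have been interchanged. The sample size margin covers roughly one-fifth of participants being lost. The rule for seeking more participants applies only after four-fifths have been lost. Between those points the study could fall well below its stated minimum without this rule calling for the meeting with the funding partner. What is at stake is the parent study's power to separate green from comparison homes.

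The screening figures raise a related but much smaller doubt: whether the planned number of screens can supply the number of households that the sample size requires.

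**Working it through.** **1. Reproduce the planned sample size.**
- Per building: 25/0.80 = 31.25, rounded up to 32.
- Per arm: 32 × 13 = 416. Both arms: 832. These match B.1.
- The base of 325 is 13 buildings × 25 apartments, from Equation 1: m = D·2(z_α + z_Q)²{1 + (n − 1)ρ}/(nΔ²), with D = 3.62, n = 3, ρ = 0.5, Δ = 0.30 and power 0.80.
- One-sided alpha 0.05: m = 3.62 × 2 × (1.645 + 0.842)² × 2/(3 × 0.09) ≈ 331.6, or 13.3 buildings. This agrees with the stated 13.
- Two-sided alpha 0.05: m ≈ 420.9, or 16.8 buildings. This does not agree. The one-sided version is therefore used below, although the text does not state the sidedness.

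**2. Loss that the design can absorb.**
- 325/416 = 78.1%, so at most 21.9% loss.
- At 20% loss: 416 × 0.80 = 332.8 per arm, still above 325.
- At 80% loss: 416 × 0.20 = 83.2 per arm, about 242 short of 325.

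**3. Power as loss rises.** Rearranging Equation 1, power = Φ(√[m·n·Δ²/(2D{1 + (n − 1)ρ})] − 1.645), where the denominator is 2 × 3.62 × 2 = 14.48.

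| Loss | Completers per arm | m × 3 × 0.09/14.48 | Power |
|---|---|---|---|
| 20% | 332.8 | 6.206 | about 80% |
| 50% | 208.0 | 3.878 | about 63% |
| 80% | 83.2 | 1.551 | about 34% |

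With two-sided alpha the same equation gives about 70% at 20% loss and 24% at 80% loss.

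**4. What the remedy would deliver.** One added site brings 32 per arm. At 80% loss that is 32 × 0.20 = 6.4 completers per arm; at 20% loss it is 32 × 0.80 = 25.6.

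**5. Screening yield (A.12).**
- 1000 × (1 − 0.20) = 800 eligible; 832 − 800 = 32 short, or 32/832 = 3.8%, assuming every eligible household joins.
- Screens needed with no refusals: 832/0.80 = 1040.
- Extra burden: 40 × 10 minutes = 400 minutes, about 6.7 hours.
- If only 800 enrolled and 20% were lost, 320 per arm would finish against 325, with power of about 79% on Equation 1.

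**The case against.** **It is only a slip.** The intended target of at least 80% completion stands in the same section, so most readers would see what was meant. That is probably true, but nothing elsewhere in the document corrects the sentence, and as written it is the operative threshold.

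**A reader might infer that attrition would go unaddressed until 80% loss.** The document does not support that. The trigger only starts a meeting that may lead to another site. Other measures run regardless: compensation paid as activities are completed, return of results at the last visit, at least ten documented contact attempts with use of alternate contacts (B.3), and quarterly reports reviewed by HUD (Table 20). What remains is that the one numerical escalation rule is set at the wrong level.

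**The 325 belongs to the allergen calculation, not to asthma.** Correct: B.1 puts the asthma requirement at 274 per arm. On that figure the design tolerates 1 − 274/416 = 34.1% loss, still far below 80%, and 83 per arm remains far too few.

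**The screening gap is small.** This also stands. The 1000 is approximate, the 20% is an estimate, both sit in a respondent-burden calculation, and B.2 allows additional town hall meetings to increase participation. A reader might infer a much larger shortfall by also applying B.1's statement, "We assume an 80% participation rate for the eligible residents for the collection as a whole": 1000 × 0.80 × 0.80 = 640 enrolled, and 832/0.64 = 1300 screens needed. That sentence, however, refers to Part B section 3, where the only 80% is completion after enrolment. The 640 and 1300 hold only if that 80% is assumed to mean consent, which the document does not say.

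**Scope.** These figures belong to the parent study. Sections 2.3 and 2.4 of the main protocol treat the add-on's sample as fixed by what the CDC grantee can recruit and retain, and Appendix D says EPA has no role in recruitment or retention. This lowers the importance of both points for the add-on, but does not make the sentence right.

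**Conclusion.** The contingency threshold in B.3 contradicts both the completion expected in the same section and the 20% loss on which 416 per arm rests. The design keeps its 325 per arm only up to 21.9% loss. At the stated trigger 83 per arm would remain, and power on Equation 1 would be about 34% instead of about 80%. The power figures assume the document's Δ, ρ and design effect, and one-sided alpha 0.05, inferred because it reproduces the 13 buildings. The contradiction itself needs none of these assumptions.

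The screening mismatch in A.12 is real but minor: 32 households, or 3.8%, before any refusals.

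Both are corrections to the 13-city plan in Appendix A. Neither shows a fault in the sample size of the 64-home add-on.

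**What to change.** In B.3, change the trigger to loss to follow-up greater than 20%, or equivalently completion below 80%. At that point about 333 per arm would remain, so the rule would act while the minimum of 325 is still met. The cost is one number.

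In A.12, restate the planned screens as at least 1040, and more if some eligible households are expected to decline, and update the screening row of the burden tables. At 1040 this adds about 7 burden hours. It would also help to say in B.1 whether the 80% participation rate means consent or completion.
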